3.6. Stopping and Subjects withdraw Criteria

The following criteria will result in immediate discontinuation of the subject dosing:

- An SAE that is related to GMA301;
- QTcF >500 msec or extension 60 msec against baseline.
- Liver function test abnormalities for severe liver injury (based upon US FDA “Guidance for Industry, Drug-Induced Liver Injury: Premarketing Clinical Evaluation”, July 2009):
 - Alanine aminotransferase (ALT) or aspartate aminotransferase (AST)>3x upper limits of normal (ULN) with total bilirubin > 2X ULN (Hy’s Law)
 - ALT or AST >3x ULN with international normalized ratio (INR)>1.5
 - ALT or AST >8X ULN
 - ALT or AST >5X ULN persisting for more than 2 weeks
 - ALT or AST >3x ULN or 3 times baseline value with the appearance of fatigue, nausea, vomiting, right upper quadrant pain or tenderness, fever, rash and/or eosinophilia (>5%)

Close follow-up of subjects must be organized in any of the above cases including:

- Repeating liver enzyme and serum bilirubin tests 2 or 3 times weekly. Frequency of retesting can decrease to once a week or less if abnormalities stabilize or the trial drug has been discontinued and the subject is asymptomatic.
- Obtaining a more detailed history of symptoms and prior or concurrent diseases
- Obtaining a history of concomitant drug use (including non-prescription medications and herbal and dietary supplement preparations), alcohol use, recreational drug use, and special diets.
- Ruling out acute viral hepatitis types A, B, C, D, and E; autoimmune or alcoholic hepatitis; non-alcoholic steatohepatitis; hypoxic/ischemic hepatopathy; and biliary tract disease.
- Obtaining a history of exposure to environmental chemical agents.
- Obtaining additional tests to evaluate liver function, as appropriate (e.g., INR, direct bilirubin)
- Obtaining gastroenterology or hepatology consultations

If a treatment-related SAE is suspected by investigators, immediate discontinuation of study drug must occur and medical care must be applied and the case immediately reported to the SRC. An ad hoc SRC meeting will be organized to make decisions for the study accordingly.

A subject is free to withdraw from the study at any time. A subject is requested to withdraw by the investigators if any of the following criteria are met:

- Subjects' non-compliance with the study procedure that might affect subject safety or study assessments/objectives, by the investigators

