5.2. Study drug Administration

The 300, 600, and 1000 mg doses of GMA301 and matching placebo will be administered Q4W via IV injection by slow push for 12 weeks.

The study drug will be injected at an approximate rate of no more than 4 mL/min. The syringes should be connected to the previously inserted cannula for administration.

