5.5. Treatment Compliance

The following measures will be employed to ensure treatment compliance:

All doses will be administered by suitably qualified study site staff.

At each dosing occasion, a pre-dose and post-dose inventory of IMP will be performed.

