7. STUDY ASSESSMENTS AND PROCEDURES

Where activities at a given timepoint coincide, consideration must be given to ensure that the following order of activities is maintained: ECGs, vital signs, and blood drawings.

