7.2.2. Clinical Laboratory Evaluations

Blood and urine samples will be collected for clinical laboratory evaluations (including clinical chemistry, hematology, urinalysis, and serology) at the times indicated in the Schedule of Assessments in [Appendix 6](#).

Clinical laboratory evaluations are listed in [Appendix 2](#). Additional clinical laboratory evaluations will be performed at other times if judged to be clinically appropriate or if the ongoing review of the data suggests a more detailed assessment of clinical laboratory safety evaluations is required.

For females of reproductive potential, a pregnancy test will be performed at the times indicated in the Schedule of Assessments in [Appendix 6](#).

An Investigator (or designee) will perform a clinical assessment of all clinical laboratory data.

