Appendix 3: Total Blood Volume

The following blood volumes will be withdrawn for each subject.

	Volume per blood sample (mL)	Maximum number of blood samples	Total amount of blood (mL)
Hematology, clinical chemistry, and coagulation	10	5	50
Serology	5	1	5
GMA301 pharmacokinetics	2	21	42
ADA	6	6	36
NT-proBNP	2.5	4	10
FSH and pregnancy test	5	1	5

Blood volumes for clinical chemistry, hematology, coagulation, serology test, FSH, and pregnancy test will meet local laboratory requirement. The volumes in above table are only for reference.

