- d. Tests can also be done on the last day of Week 11. If a subject discontinues the visit in advance, it would be better to ask the subject to complete the Week 12 examinations.
- e. Serology tests refer to Hepatitis B surface antigen, Hepatitis C antibody, and Human Immunodeficiency Virus antibodies ([Appendix 2](#)).
- f. Women of childbearing potential will perform pregnancy test in serum at Screening and in urine at randomization and Weeks 4, 8, and 12.
- g. FSH test will be performed at the same time with serum pregnancy test at Screening.
- h. ADA will be collected at: Week 0 (pre-dose of the 1st dose), Week 2, Week 4 (prior to 2nd dose), Week 8 (prior to 3rd dose), Week 12 and Week 18 (end of follow-up).

Pharmacokinetics sampling:

Pharmacokinetics serum samples will be obtained for PK assessments at the following timepoints (\pm Time window):

[figure not shown]
Dose 1st: predose, 4 (\pm 15 min), 8 (\pm 30 min), 24 (\pm 120 min), 72 (\pm 240 min), 168 (Day 8; \pm 480 min), 336 (Day 15; \pm 1 day), 504 (Day 22; \pm 1 day), and 672 (Day 29; \pm 1 day) hours post dose.

Dose 3rd: predose, 4 (\pm 15 min), 8 (\pm 30 min), 24 (\pm 120 min), 72 (\pm 240 min), 168 (Day 8; \pm 480 min), 336 (Day 15; \pm 1 Day), 504 (Day 22; \pm 1 day), 672 (Day 29; \pm 1 day), 1008 (Day 43; \pm 2 day), 1344 (Day 57; \pm 3 day), 1680 (Day 71; \pm 3 day) hours postdose.

The samples of the 672h post 1st dose will be collected before the 2nd dose.

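### The Week 4 and Week 8 urine pregnancy tests need not be negative before the injection, and a positive test is not a mandatory dosing stop in section 3.6

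*Combined protocol and SAP*

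**What the plan says.** - Section 3.1 and Table 2 place the three injections at Week 0, Week 4 and Week 8.
- Section 3.6 heads its individual dosing stops with "The following criteria will result in immediate discontinuation of the subject dosing". The items are a GMA301-related SAE, QTcF limits and five liver-test criteria. The section also requires stopping for a suspected treatment-related SAE. Pregnancy does not appear.
- Appendix 6, footnote f, schedules a serum pregnancy test at Screening and urine tests at randomization and Weeks 4, 8 and 12 for women of childbearing potential. It gives no order relative to the injection.
- Section 7 asks that "the following order of activities is maintained: ECGs, vital signs, and blood drawings". The injection and the urine test are not in that sequence.
- Section 5.5 states: "At each dosing occasion, a pre-dose and post-dose inventory of IMP will be performed". That is the only pre-dose step it names. Section 5.2 covers dose, route and rate ("The study drug will be injected at an approximate rate of no more than 4 mL/min").
- Appendix 1 treats pregnancy as outside the definition of an adverse event and asks for it to be reported through the SAE route.
- Pre-dose timing is written for other samples. ADA blood, for instance, is due at "Week 4 (prior to 2nd dose), Week 8 (prior to 3rd dose").

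**The concern.** A scheduled safety test protects a subject only if its result can change what happens next. Here the test falls on the dosing visit, the result need not be known before the injection, and no mandatory consequence follows a positive result.

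An IV dose cannot be taken back. Section 1.5.2 reports mean terminal half-lives of 503.75 to 565.63 hours in healthy subjects, or about 21 to 24 days (503.75/24 = 21.0; 565.63/24 = 23.6). Section 1.1 describes GMA301 as an antibody against endothelin receptor type A, and section 1 records fetal-toxicity concerns for all endothelin receptor antagonists. The protocol does not show whether that concern carries over to this antibody, but it is reason enough to close the gap when doing so is nearly free.

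**Working it through.** No figure in the plan is in dispute. The check compares the provisions and then counts doses.

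**Step 1. Is the test placed before the injection?** Section 7 orders ECG, vital signs and blood draws only. Sections 5.2 and 5.5 do not mention it. Footnote f gives visits, not order. Pre-dose wording exists for Week 0 samples (footnote c), ADA (footnote h) and PK (predose samples at doses 1 and 3; the 672-hour sample before dose 2). None of these covers the urine test at Weeks 4 and 8.

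**Step 2. Does any provision make a positive test stop dosing?**

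- Section 3.6 dosing stops: pregnancy is not listed.
- SAE stop: not triggered by pregnancy itself, because Appendix 1 says pregnancy is not an adverse event.
- Exclusion 19: bars pregnant women, but as an eligibility criterion.
- Contraception (inclusion 10) with the non-compliance withdrawal in section 3.6: reaches a subject who did not comply, not one who complied and whose method failed.
- Withdrawal for clinically relevant signs or symptoms in section 3.6: rests on investigator opinion.
- Appendix 1: reporting, and education before consent.

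**Step 3. Further doses after a positive test.** Doses remaining at a visit = 3 planned − doses already given. Week 4: 3 − 1 = 2. Week 8: 3 − 2 = 1. Subtract the doses that a mandatory rule blocks:

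| Rules in force | Positive at Week 4 | Positive at Week 8 |
|---|---|---|
| As written | 2 − 0 = 2 | 1 − 0 = 1 |
| Positive test added to 3.6, but read after the injection | 2 − 1 = 1 | 1 − 0 = 1 |
| Negative test required first, and positive test added to 3.6 | 2 − 2 = 0 | 1 − 1 = 0 |

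The first two rows are upper limits, assuming no discretionary action. Both changes are needed: a stop without an order still allows one dose.

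**Step 4. Reach.** Planned injections: 36 × 3 = 108, of which 36 × 2 = 72 are at Weeks 4 and 8. Active: 27 × 3 = 81, of which 27 × 2 = 54. These are all-subject totals if everyone completes dosing. The pregnancy rule covers only the part given to women of childbearing potential, whose number is not stated.

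**Step 5. The same timing question for liver tests (secondary).** Appendix 3 allows five safety blood samples, consistent with Screening, Day -1 and Weeks 4, 8 and 12. Section 7.2.2 says "An Investigator (or designee) will perform a clinical assessment of all clinical laboratory data", with no time relative to dosing. If results are read after the injection, the Week 4 panel can stop only dose 3 and the Week 8 panel can stop no dose. The newest scheduled result in hand at dose 3 is then 57 − 29 = 28 days old, with a range from 56 − 30 = 26 to 58 − 28 = 30 under the ±1 day windows. This assumes no unscheduled test.

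**The case against.** The strongest reply is that the protocol already surrounds pregnancy with safeguards: an entry exclusion not expressly limited to Screening, required contraception, formal education before consent, repeated testing, SAE-route reporting and investigator discretion to withdraw. A careful investigator would read the urine test first and would not dose after a positive result. A rule may also exist in the SRC charter or site operations document, which are not available here. All of this lowers the chance of harm. None of it is a mandatory stop in the protocol.

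A reader might infer that sites do inject before reading, or that doing so would breach section 3.6. The documents support neither: they do not describe site practice, and section 3.6 acts once a criterion is known to be met. A reader might also take 72 of 108 as a count of injections at risk. It is not. It includes 9 × 2 = 18 placebo injections and all subjects who could not be pregnant.

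It is also tempting to give the liver timing equal weight. The objection there largely stands:

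- No GMA301 liver signal is reported in the monkey studies or among the most frequent events in healthy subjects.
- Subjects with ALT or AST at or above 2 times ULN are excluded at entry.
- The four-weekly panels are in line with the strictest schedule that section 1 describes for the class, the monthly testing required for bosentan.
- Section 7.2.2 adds "Additional clinical laboratory evaluations will be performed at other times if judged to be clinically appropriate".
- Requiring a result in hand could mean an extra visit or a delayed dose, and a delay would shift the interval behind trough, AUC over the dosing interval and accumulation ratio.

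**Conclusion.** The pregnancy point holds. As written, a subject who becomes pregnant despite complying with contraception can receive up to two further injections if positive at Week 4, or one if positive at Week 8, without any departure from the protocol. This is an inexpensive safety improvement that should be made. It does not show that any subject would be harmed, and it changes no endpoint or analysis.

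The conclusion rests on the protocol text alone. No pregnancy rate, liver-event rate or fetal effect of GMA301 is claimed, because the documents give none. The schedule grid is broken in the available text, so the Week 4 and Week 8 pregnancy tests are taken from footnote f, and the liver-panel visits from the grid together with the five-sample limit.

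The liver timing is a real gap in the wording, but closing it is a trade-off. The liver stop acts one dose late only if a site injects before reading, so it stays an optional addition.

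**What to change.** **Main change.** In Appendix 6, footnote f, require a negative urine pregnancy test before the first dose and before the Week 4 and Week 8 injections in women of childbearing potential. In section 3.6, add a positive pregnancy test to the mandatory dosing stops. No test is added, since urine tests are already scheduled at randomization and Weeks 4 and 8. The cost is amendment wording and a few minutes' wait at each visit.

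**Optional.** Where a result is available the same day, or from a draw up to 3 days earlier (the allowance footnote a gives at Week 0), review ALT, AST, bilirubin and INR against the existing section 3.6 criteria before doses 2 and 3. Blood is already drawn before both injections for ADA, so a same-day draw is feasible; the open question is when the result is read. Appendix 3 points to local laboratories ("Blood volumes for clinical chemistry, hematology, coagulation, serology test, FSH, and pregnancy test will meet local laboratory requirement"), but no turnaround time is given. A draw 2 or 3 days ahead would usually fall outside the ±1 day visit window, so the schedule would have to allow it. The cost is a wait at the visit, or up to two extra visits with the 8-hour fast of section 6.2 for patients in functional class II to III. Sites that cannot obtain results in time should not be made to delay doses for this.

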4. SELECTION OF STUDY POPULATION

4.1. Inclusion Criteria

Subjects must meet all of the following criteria:

1. Male or female, aged 18 to 75 years inclusive
2. WHO Group 1 PAH related to one of the following conditions:
 - a. Idiopathic
 - b. Heritable
 - c. Drugs or toxins-induced
 - d. Associated with connective tissue disease
 - e. Associated with congenital heart disease if subjects underwent surgical correction more than 12 months before Screening
3. Symptoms due to PAH are consistent with WHO functional class II- III
4. Have not taken endothelin receptor antagonists (ERAs) within 3 months before randomization.
5. Has been taking at least one oral PAH targeted drug that has been approved by local guidelines for at least 3 months before screening with a stable dosage and the disease did not worsen during this period.

6. Right heart catheterization (RHC) result meets below criteria when screening.
 - a. Mean pulmonary arterial pressure (PAP) ≥ 25 mmHg
 - b. Pulmonary vascular resistance (PVR) > 3 Woods units
 - c. PA wedge pressure (PAWP) ≤ 15 mmHg

if subject has undergone RHC within 3 months before screening, the waveform results will serve as baseline data if they meet entry criteria and the RHC at Screening will not be repeated.

7. Has a six-minute walk test (6MWT) with distance between 150 to 450 meters at Screening.
8. The dosage of digitalis drugs or L-arginine supplementation, if applicable, must be stable for at least 1 month before Screening.
9. No new use of an IV diuretic, cardiotonic, or vasoactive drug within 30 days before screening.
10. Both male and female subjects agree to use a medically acceptable method of contraception throughout the entire study period from informed consent signing to 90 days after last dose, if the possibility of conception exists. Medically acceptable methods of contraception include oral, implantable, or injectable contraceptives (starting 2 months before dosing); diaphragm with vaginal spermicide; intrauterine device; condom and partner using vaginal spermicide; and surgical sterilization (6 months after surgery). Women who are surgically sterile or those who are postmenopausal for at least 2 years are not considered to be of childbearing potential. Eligible male and female subjects must agree not to participate in a conception process (i.e. active attempt to become pregnant or to impregnate, sperm donation, in vitro fertilization) during the study and for 90 days after the last dose of study drug.
11. Body weight no less than 40 kg at Screening.
12. Able to understand and willing to sign the Informed Consent Form (ICF) and comply with the study procedures.

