10. Both male and female subjects agree to use a medically acceptable method of contraception throughout the entire study period from informed consent signing to 90 days after last dose, if the possibility of conception exists. Medically acceptable methods of contraception include oral, implantable, or injectable contraceptives (starting 2 months before dosing); diaphragm with vaginal spermicide; intrauterine device; condom and partner using vaginal spermicide; and surgical sterilization (6 months after surgery). Women who are surgically sterile or those who are postmenopausal for at least 2 years are not considered to be of childbearing potential. Eligible male and female subjects must agree not to participate in a

conception process (i.e. active attempt to become pregnant or to impregnate, sperm donation, in vitro fertilization) during the study and for 90 days after the last dose of study drug.

11. Body weight no less than 40 kg at Screening.
12. Able to understand and willing to sign the Informed Consent Form (ICF) and comply with the study procedures.

Exclusion Criteria

Subjects who meet any of the following criteria will not be allowed to participate in this study:

1. Diagnosed with WHO Group II, III, IV, V of PH;
2. Using calcium channel blockers when Screening;
3. BP>160/100mmHg at Screening;
4. Systolic BP <90 mmHg at Screening;
5. Pulmonary function test: FEV1<60% of predicted, TLC<60% of predicted, DLCO<60% of predicted;
6. One of the following tests with confirmed pulmonary embolism and/or chronic thrombo-embolic pulmonary hypertension (CTEPH) following initial diagnosis of PAH:
 - a. Pulmonary ventilation/perfusion scan
 - b. CT pulmonary angiogram
 - c. Contrast dye pulmonary angiogram
7. History of sleep apnea.
8. Limited full participation in the 6MWT due to arthritic, neuromuscular, vascular or other diseases unrelated to PAH.
9. History of acute cardiovascular and/or cerebrovascular events within 6 months before screening.
10. Echocardiogram (ECHO) demonstrating at least one of the following:
 - a. LVEF $\leq 50\%$
 - b. Mean end-diastolic left ventricular septal and posterior wall thickness of >12 mm
 - c. Left atrial (LA) area on apical 4 chamber view >20 cm^2
 - d. LA volume by biplane modified Simpsons or area-length methods >55 mL
 - e. LA volume index >29 mL/m 2

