- Any clinically relevant sign or symptom (eg, Class IV heart failure) that, in the opinion of the Investigator (or designee), warrants subject withdrawal.

Subject who didn't get IMP treatment within protocol defined timeline with any reason can get back to the IMP treatment with investigator or SRC's evaluation and agreement.

All the discontinuation must be documented accordingly. If a subject is withdrawn, the Sponsor will be notified in 24 hours and the date and reason(s) for the withdrawal will be documented in electronic Case Report Form (eCRF). In this case, efforts in any ways must be made to complete the follow up assessments. ([Appendix 6](#)). Other medical procedures may be performed at the Investigator's discretion. The Investigator may also request subjects to return for additional Follow-up visits. All AEs will be followed until recovery or stabilization.

Cohort discontinuation and study termination

The SRC will discontinue or stop the cohort or even the study in case of :

- Two cases discontinuations in a cohort due to events related to the study drug under the diagnosis of the investigators;
- Single case with severe allergic event related to study drug;
- Known and expected AEs are with increased frequency, severity and or long lasting.

The sponsor can terminate the study with notification to the investigators.

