Appendix 4: Contraception Guidance

Definitions

Women of Childbearing Potential: premenopausal females who are anatomically and physiologically capable of becoming pregnant following menarche.

Women of Nonchildbearing Potential:

1. **Surgically sterile:** females who are permanently sterile via hysterectomy, bilateral salpingectomy, and/or bilateral oophorectomy by reported medical history and/or medical records. Surgical sterilization to have occurred a minimum of 6 weeks, or at the Investigator's discretion, prior to Screening.
2. **Postmenopausal:** Females at least 45 years of age with amenorrhea for 12 months without an alternative medical reason with confirmatory follicle-stimulating hormone (FSH) levels of ≥ 40 mIU/mL. The amenorrhea should not be induced by a medical condition such as anorexia nervosa, hypothyroid disease or polycystic ovarian disease, or by extreme exercise. It should not be due to concomitant medications that may have induced the amenorrhea such as oral contraceptives, hormones, gonadotropin-releasing hormones, anti-estrogens, or selective estrogen receptor modulators.

Fertile male: a male that is considered fertile after puberty.

Infertile male: permanently sterile male via bilateral orchiectomy.

Contraception Guidance

Female Subjects

Female subjects who are of nonchildbearing potential will not be required to use contraception. Female subjects of childbearing potential must be willing to use an acceptable method of birth control from the time of signing the informed consent form until 90 days after the Follow-up visit. Acceptable methods of contraception include:

- hormonal injection (as prescribed)
- combined oral contraceptive pill or progestin/progestogen-only pill (as prescribed)
- combined hormonal patch (as prescribed)
- combined hormonal vaginal ring (as prescribed)
- surgical method performed at least 3 months prior to the Screening visit:
 - bilateral tubal ligation
 - Essure® (hysteroscopic bilateral tubal occlusion) with confirmation of occlusion of the fallopian tubes
- hormonal implant

- hormonal or non-hormonal intrauterine device
- male condom with spermicide
- female condom with spermicide
- over-the-counter sponge with spermicide
- cervical cap with spermicide (as prescribed)
- diaphragm with spermicide (as prescribed)

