- vasectomized male partner (sterilization performed at least 90 days prior to the Screening visit, with verbal confirmation of surgical success, and the sole partner for the female subject).

Female subjects of childbearing potential should refrain from donation of ova from Check-in (Day -1) until 90 days after the Follow-up visit.

Male Subjects

Male subjects will be surgically sterile for at least 90 days, with documented azoospermia, or when sexually active with female partners of childbearing potential will be required to use a male condom with spermicide (even if participant has a history of vasectomy) from Check-in until 90 days after the Follow-up visit. Sexual intercourse with female partners who are pregnant or breastfeeding should be avoided unless condoms are used from the time of the first dose until 90 days after the Follow-up visit. Male subjects are required to refrain from donation of sperm from Check-in until 90 days after the Follow-up visit.

Sexual Abstinence and Same-sex Relationships

Subjects who practice true abstinence, because of the subject's lifestyle choice (ie, the subject should not become abstinent just for the purpose of study participation), are exempt from contraceptive requirements. Periodic abstinence (eg, calendar, ovulation, symptothermal, postovulation methods) and withdrawal are not acceptable methods of contraception. If a subject who is abstinent at the time of signing the ICF becomes sexually active they must agree to use contraception as described previously.

For subjects who are exclusively in same-sex relationships, contraceptive requirements do not apply. If a subject who is in a same-sex relationship at the time of signing the ICF becomes engaged in a heterosexual relationship, they must agree to use contraception as described previously.

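### Inclusion 10 and the synopsis end contraception 90 days after the last dose, Appendix 4 ends it 90 days after the Follow-up visit (nominally 70 days later for completers), and no text says which governs.

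*Combined protocol and SAP*

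**What the plan says.** **End dates.** Inclusion 10 (section 4.1) asks both sexes for contraception "throughout the entire study period from informed consent signing to 90 days after last dose", and the synopsis has the same rule. A second clause of inclusion 10 bars attempts at conception and sperm donation "during the study and for 90 days after the last dose of study drug".

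Appendix 4 asks women of childbearing potential for contraception "from the time of signing the informed consent form until 90 days after the Follow-up visit". It adds that they "should refrain from donation of ova from Check-in (Day -1) until 90 days after the Follow-up visit". Its contraception rule for men has the same end point, and "Male subjects are required to refrain from donation of sperm from Check-in until 90 days after the Follow-up visit".

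**Which visit.** Appendix 4 speaks of one Follow-up visit, whereas the Appendix 6 schedule has three, at Weeks 14, 16 and 18. Footnote h to that schedule closes its list of antibody sampling times with "Week 12 and Week 18 (end of follow-up"), which marks Week 18 as the last.

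**Precedence.** Section 4.1 does not refer to Appendix 4. Apart from the table of contents, no text cites that appendix, and nothing gives an order of precedence.

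**Who is covered.** Inclusion 10 treats a woman as not of childbearing potential after two years of menopause. Appendix 4 requires age 45 or over, 12 months' amenorrhea and a confirmatory FSH level. For sterilisation as a contraceptive method, inclusion 10 states six months after surgery and Appendix 4 three months before Screening.

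**The concern.** The Introduction records fetal toxicity concerns for all endothelin receptor antagonists, and section 1.1 describes GMA301 as an antibody against the endothelin type A receptor. How long subjects must avoid conception is therefore a real safety rule, and the protocol gives it two end dates.

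The practical risk runs one way. A site working from the eligibility list or the synopsis would release subjects earlier than Appendix 4 allows, and would breach that appendix without knowing it. The rules also diverge after scheduled contact has ended. The last scheduled pregnancy test is at Week 12 (Day 85) and the last visit at Week 18 (Day 127), both before even the shorter rule expires. No later visit would correct a wrong date.

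**Working it through.** **Inputs**
- Dosing days: Day 1, Day 29±1, Day 57±1 (Appendix 6).
- Follow-up visits: Week 14 = Day 99±3, Week 16 = Day 113±3, Week 18 = Day 127±3 (Appendix 6).
- Mean terminal half-life: 503.75 to 565.63 h, from single doses in healthy subjects (section 1.5.2).

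**The plan's own interval.** Appendix 6 places the final pharmacokinetic sample 1680 h after the third dose. 1680/24 = 70 days, and 127 - 57 = 70 days. The two agree.

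**Completers**
- Inclusion 10 and synopsis: 57 + 90 = Day 147.
- Appendix 4, Week 18 meant: 127 + 90 = Day 217.
- Gap: 217 - 147 = 70 days. The 90 cancels, so the gap is simply the time from last dose to Follow-up visit.
- With windows: 124 - 58 = 66 to 130 - 56 = 74 days.
- If Week 14 were meant: 99 - 57 = 42 days. If Week 16: 113 - 57 = 56 days. No reading brings the gap to zero.
- The references to the study period in inclusion 10 do not help, because a completer's study ends on Day 127, before Day 147.

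**Subjects who stop dosing early but are followed to Week 18.** Section 3.6 says of withdrawn subjects that "efforts in any ways must be made to complete the follow up assessments", so such subjects are expected.

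| Last dose | 90 days after it | Appendix 4 | Gap if the clause stops there | Gap if the clause runs at least to Week 18 |
|---|---|---|---|---|
| Day 29 | Day 119 | Day 217 | 98 (94 to 102) | 217 - 127 = 90 |
| Day 1 | Day 91 | Day 217 | 126 (123 to 129) | 217 - 127 = 90 |

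The no-conception and sperm-donation clause covers the study itself as well as the 90 days, so the last column applies to it on its plain words. The contraception clause can be read either way: its study period may be defined by the 90 days, or may extend to Week 18.

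**Exposure at each end date (completers).** Assume mono-exponential decline with the healthy-subject half-life t. Fraction of the post-last-dose level = 2^(-24 × days / t).
- 90 days = 2160 h: 2160/565.63 = 3.82 and 2160/503.75 = 4.29 half-lives, leaving 7.1% and 5.1%.
- 70 + 90 = 160 days = 3840 h: 3840/565.63 = 6.79 and 3840/503.75 = 7.62 half-lives, leaving 0.9% and 0.5%.

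**The case against.** The best defence is that the two rules can be obeyed together. With Week 18 as the visit, anyone who meets Appendix 4's end date also meets inclusion 10's, and inclusion 12 requires willingness to follow study procedures. Appendix 1 provides formal education of women of childbearing potential before consent, and reporting of any pregnancy through the SAE process. The consent form is not among the documents and may give a single clear date. These points limit the severity. They do not remove the problem, because none of the safeguards we can read states an end date.

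A reader might go further than the documents allow in three ways.

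- *That every early stopper faces a gap of 98 or 126 days.* The no-conception clause already runs through the study, so its gap is 90 days. The larger figures hold only for the contraception clause, on one reading, and only if Week 18 is attended.
- *That the shorter rule exposes a fetus to harm.* The percentages describe drug remaining, extrapolated from single doses in healthy subjects. No effect threshold is given for any level.
- *That the coverage criteria put identifiable women on opposite sides.* Appendix 4 defines childbearing potential as premenopausal but sets a minimum age of 45 for postmenopausal status. A younger postmenopausal woman is therefore unclassified, not clearly covered. Inclusion 10 applies only where conception is possible, and does not say from which date its six months is counted. What is shown is that the criteria differ.

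**Conclusion.** The inconsistency stands, between current operative texts. For completers the end dates differ by 70 days nominally, 66 to 74 within scheduled windows. The range does not cover doses resumed off schedule or extra follow-up visits, both of which section 3.6 permits. The figure takes the Follow-up visit as Week 18; the other two visits would give 42 or 56 days. For early stoppers followed to Week 18, the gap is 90 days for the no-conception clause, and either 90 or 98/126 days for the contraception clause.

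If the healthy-subject half-life and mono-exponential decline carry over to PAH subjects on repeat dosing, the shorter rule ends at 3.8 to 4.3 half-lives and the longer at 6.8 to 7.6. That is reason enough to settle on the longer one. Severity is minor to moderate: it concerns subject protection and site compliance, and touches no endpoint or analysis.

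**What to change.** Align inclusion 10 and the synopsis to Appendix 4, for women and men, and for contraception, conception, and ova and sperm donation alike. Define the Follow-up visit as the Week 18 visit. A subject who misses Week 18 would then have no date under Appendix 4, so use 160 days after the last dose, which equals the completer's nominal interval (57 + 160 = Day 217). If one sentence for everyone is preferred, use the later of 160 days after the last dose and 90 days after the Week 18 visit.

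A plain rule of 160 days after the last dose for all would be simpler but should not be used. For early stoppers who attend Week 18 it ends on Day 29 + 160 = 189 or Day 1 + 160 = 161, which is 28 or 56 days before Appendix 4's Day 217. With the rule proposed here, nobody's period is shorter than under inclusion 10, or than under Appendix 4 read as Week 18.

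In the same amendment, adopt one definition of postmenopausal status and one sterilisation lead time in both places.

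The cost is a wording amendment with IRB/EC approval, regulatory approval where locally required, and re-consent of current subjects (Appendix 5). Completers use contraception about 70 days longer than inclusion 10 now asks, which may deter a few candidates. Visits, sample size and analysis do not change.
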